8.3 Subgroup Analyses

For mortality and morbidity outcomes, there will be assessment of outcomes by other ages and of outcomes assessed in more specific ways, as also outlined above.

- The composite outcome of all-cause mortality and non-fatal admission with infection by 42 days of age and by 2 years of age
- All-cause mortality by 42 days of age and 2 years of age.
- In-hospital case-fatality for all-cause and infectious disease admissions by 42 days of age and 2 years of age.
- Morbidity: hospital admissions and in-hospital case-fatality rate for major diseases groups (sepsis, respiratory infections, bronchitis, diarrheal diseases, malaria, malnutrition-related diseases) by 42 days of age and by 2 years of age.

Potential effect modification

Based on literature-identified potential effect modifiers, we will assess whether the effect of HBV0 is modified by the following potential effect modifiers (in addition to sex): vaccination campaigns, the BCG scar status of the mother at enrollment, inclusion weight ($\geq 2,500\text{g}$, between $\geq 2,000\text{g}$ to $<2,500\text{g}$, and $<2,000\text{g}$), season, mode of delivery (vaginal or Caesarean section) and whether the baby was born at a hospital or elsewhere. We will conduct a supplementary analysis to assess

HBV0's effects by age at enrolment (within 24 hours and ≥ 24 hours after birth), our hypothesis being that HBV0 will have the most marked effects among the youngest neonates. For the composite outcome by 42 days of age and by 2 years of age, we will calculate the female/male ratio.

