4.3 Primary and Secondary Outcome Measures

Primary outcome: Mortality and morbidity

The composite outcome of all-cause mortality or first non-fatal admission with infection from randomization to 42 days of age (before the next routine vaccination) in the group given HBV0 compared with the control group.

Secondary outcomes: Neurodevelopmental disorders and AD

AD by 2 years of age

In a subgroup followed to 2 years of age (see sample size calculation): cumulative incidence of AD symptoms (self-reported at home visits or telephone follow-up) and cumulative incidence of AD diagnosed by an MD with special training.

Neurodevelopment by 5 years of age

In a subgroup of 500 singleton children from the HDSS followed to 5 years of age: cognitive outcomes assessed by the Mullen Scales of Early Learning and the Kaufman Assessment Battery for Children. These tests have been tested for validity in Sub-Saharan African children.[49–52]

The outcomes will be further explored to assess the effect by subcategory of outcome and by age (**Table 2**).

Table 2. Trial outcomes and data sources

Primary outcome	Whom	Age assessed	Data source(s)
Composite outcome: all-cause mortality and admission due to non-fatal infection	All infants	6 weeks	A, B, C
Secondary outcomes			
I: Self-reported AD and II: physician-diagnosed AD	I: All infants. II: To 200 cases among controls*	2 years	A, B, D
Neurodevelopmental outcomes	500 HDSS children*	5 years	E
Outcome subcategories and by age			
Composite outcome: all-cause mortality and admission due to non-fatal infection	All infants	2 years	A, B, C
All-cause mortality	All infants	6 weeks, 2 years	A, B, C
In-hospital case-fatality (all-cause, infectious diseases)	Hospitalized infants	6 weeks, 2 years	C
Hospital admission for major diseases groups (neonatal conditions aside from sepsis, respiratory infections, bronchitis, diarrheal diseases, malaria, malnutrition-related diseases)	All infants	6 weeks, 2 years	C

* See sample size calculation section below for further information.

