8 STATISTICAL METHODS

8.1 Population to be analyzed

Data analysis will be conducted as intention-to-treat including all participants as randomized, apart from participants whose parents have withdrawn consent for their child's data to be used as part of this study, who will be excluded from analysis.

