8.2 Statistical Analysis

The Statistical Analysis Plan (SAP) will be drafted by the trial group and submitted to the DSMB for approval. Upon approval and before initiation of data analysis, the SAP will be uploaded to an online repository. When requested by the DSMB, the trial data can be unblinded, analyzed and reported according to the SAP.

The primary endpoint for the trial will be the composite outcome of all-cause mortality and first non-fatal infectious disease admission up to 42 days of age with censoring at the time of an event, loss to follow-up, or by 42 days of age, whichever comes first. Cumulative curves for mortality and hospitalization risk will be computed using the mean cumulative function, overall, and by sex. Person-years of risk will be calculated from enrollment (day, hour and minute of randomization).

The risk of the single-event composite outcome (all-cause mortality or first non-fatal admission with infection) will be estimated using Cox proportional hazards models with age as the underlying time scale, thus inherently adjusted for age. The Cox models will provide hazard ratios (HRs) from single-event analyses of the composite outcome (all-cause mortality or first non-fatal admission with infection) up to 42 days of age (primary endpoint). Incidence rate ratios for secondary endpoints relating to long-term follow-up for mortality and admissions will be estimated using recurrent-event Andersen-Gill Cox proportional hazards models with robust standard errors. Infants will not be considered at risk of admission while admitted. Randomization will be stratified by sex and place of enrollment in blocks of 24; we will therefore include different underlying baseline hazard functions by sex and place of enrollment in the Cox models. The Cox regression models will have age as the underlying time scale and account for the survival interdependency among twin pairs by using the Stata cluster command.

Tests for proportionality of hazard rates will be computed using Schoenfeld residuals, and by visual inspection of cumulative risk curves drawn using the Kaplan-Meier method.

In-hospital case-fatality risk will be estimated using binomial regression providing risk ratios (RRs), also using the Stata cluster command. In case there are fewer than five events in one group, Fisher's exact test will be used to compute a p-value.

Cognitive scores will be standardized and tested using linear regression models.

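### In-hospital case-fatality is compared between arms among admitted infants only, so the risk ratio is not a randomised effect and can mislead in either direction; the disease-group lists also disagree on sepsis

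*Protocol*

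**What the plan says.** Protocol 8.3 plans "In-hospital case-fatality for all-cause and infectious disease admissions by 42 days of age and 2 years of age". In Protocol 4.3, Table 2, the column that says in whom each outcome is assessed reads "Hospitalized infants" for this row, with hospital surveillance as the only data source. Protocol 8.2 fixes the method: "In-hospital case-fatality risk will be estimated using binomial regression providing risk ratios (RRs), also using the Stata cluster command", with Fisher's exact test when one group has fewer than five events. Protocol 8.1 sets the general analysis population: "Data analysis will be conducted as intention-to-treat including all participants as randomized".

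The disease groups appear twice. Table 2 plans "Hospital admission for major diseases groups (neonatal conditions aside from sepsis, respiratory infections, bronchitis, diarrheal diseases, malaria, malnutrition-related diseases". Section 8.3 plans "hospital admissions and in-hospital case-fatality rate for major diseases groups (sepsis, respiratory infections, bronchitis, diarrheal diseases, malaria, malnutrition-related diseases". The second list therefore also adds case-fatality by disease group, where Table 2 has admissions only.

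**The concern.** Non-fatal admission with infection is one of the two components of the primary outcome, so the trial exists partly to find out whether HBV0 changes it. If it does, the admitted infants in the two arms are differently selected, and randomisation no longer protects a comparison made among them. A ratio of case-fatality risks then mixes any effect on dying with any effect on who is admitted.

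A difference in admissions is plausible on the protocol's own description. There is no placebo, and mothers know the allocation (4.1, 6.4), so care-seeking could differ between arms. Section 7 puts fever and malaise among the most common HBV0 reactions, although it calls all the listed events rare or very rare.

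At stake is the reading of infectious and disease-group case-fatality. Neither Table 2 nor 8.3 lists infectious or disease-specific death per randomised infant, so these ratios have no randomised result beside them.

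The second matter is one of consistency. Both lists describe admissions by major disease group, and they differ on whether sepsis is a group.

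**Working it through.** **The plan's own figure.** The protocol gives no number for in-hospital case-fatality. Its sample size does reproduce: 0.04 against 0.0312, two-sided 5%, 80% power, with continuity correction, gives 7,184 per arm and 14,368 in total. This confirms the input rates but does not bear on the point.

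**Inputs for the illustration, to 42 days**
- Infants per arm: 7,250 (4.4).
- Control-group non-fatal infection admissions: 2.6% (4.4), or 0.026 × 7,250 = 188.5.
- Control-group deaths: 1.4% (4.4), or 0.014 × 7,250 = 101.5.
- Share of deaths that occur in hospital: not given. Assumed 25% to 100%, that is 0.35% to 1.4% of infants, or 25.4 to 101.5 deaths.

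**Formula.** Let d be in-hospital deaths and s non-fatal admissions, both in per cent of infants. Control case-fatality is d/(d + s): 0.35/2.95 = 11.9% up to 1.4/4.0 = 35.0%. If HBV0 multiplies s by m and leaves d unchanged, the planned ratio is

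RR = [d/(d + m·s)] / [d/(d + s)] = (d + s)/(d + m·s).

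| Scenario, deaths unchanged | d = 0.35% | d = 1.4% |
|---|---|---|
| 25% more non-fatal admissions (m = 1.25, m·s = 3.25) | 2.95/3.60 = 0.82 | 4.00/4.65 = 0.86 |
| 22% fewer non-fatal admissions (m = 0.78, m·s = 2.028) | 2.95/2.378 = 1.24 | 4.00/3.428 = 1.17 |

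In every cell, in-hospital deaths per randomised infant give RR = 1.00.

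**When the added admissions also bring deaths.** Let total admissions rise by 25%, and let the added ones have k times the control case-fatality. Then RR = (1 + 0.25k)/1.25, while in-hospital deaths per randomised infant are multiplied by 1 + 0.25k.

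| k | Case-fatality RR | In-hospital deaths per randomised infant |
|---|---|---|
| 0.5 | 1.125/1.25 = 0.90 | up 12.5% |
| 1 | 1.25/1.25 = 1.00 | up 25% |
| 2 | 1.50/1.25 = 1.20 | up 50% |

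The ratio falls below 1 only when the added admissions are less fatal than the usual ones. At equal fatality it shows nothing while deaths rise.

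**Precision.** For the 25% scenario the standard error of log RR is √(1/D − 1/A₀ + 1/D − 1/A₁), where D is deaths per arm and A₀, A₁ are admissions.
- d = 0.35%: D = 25.4, A₀ = 213.9, A₁ = 261.0. RR 0.82, 95% CI 0.49 to 1.38.
- d = 1.4%: D = 101.5, A₀ = 290.0, A₁ = 337.1. RR 0.86, 95% CI 0.69 to 1.08.

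**The two disease lists side by side**

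| Group | Table 2 | 8.3 |
|---|---|---|
| Sepsis | no | yes |
| Neonatal conditions other than sepsis | yes | no |
| Respiratory infections, bronchitis, diarrhoea, malaria, malnutrition | yes | yes |

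**The case against.** A good deal can be said for the plan. Case-fatality is neither primary nor secondary; Table 2 puts it among subcategories for further exploration and states its denominator openly. All-cause mortality, the composite and admissions by disease group are all analysed in all infants. In the 25% scenario the composite would go from 4.0% to 1.4 + 3.25 = 4.65%, a ratio of 1.16, with mortality unchanged, so a reader would see the extra admissions beside the case-fatality ratio. The intervals above include 1, so the distortion alone would be unlikely to appear as a significant finding. All of this stands and lowers the priority. It does not cover infectious and disease-group fatality, which have no all-randomised counterpart.

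The illustration is also rough. The share of deaths in hospital is assumed, and the upper end puts every death there. It sets deaths from any cause against non-fatal admissions with infection only, which matches neither planned case-fatality analysis exactly. It shows how the ratio behaves and does not predict a result.

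Three stronger readings are tempting, and the documents do not support them. A reader might infer that more admissions under HBV0 would always look like protection; the second table shows that this depends on how fatal the added admissions are. A reader might infer that sepsis is the expected route of HBV0's non-specific effects; section 2.1 links sepsis to BCG and respiratory infections to OPV, and names no route for HBV0. A reader might infer that the two lists leave sepsis to be chosen after the data are seen; 8.2 requires an SAP approved by the DSMB and uploaded before analysis, and the statistician is blinded (6.4).

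Finally, the Table 2 wording "neonatal conditions aside from sepsis, respiratory infections, bronchitis, diarrheal diseases, malaria, malnutrition-related diseases" could mean in addition to sepsis. Even so, 8.3 has "sepsis, respiratory infections, bronchitis, diarrheal diseases, malaria, malnutrition-related diseases" and no group for other neonatal conditions, so the lists still differ.

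**Conclusion.** The point holds in limited form. The protocol fixes a between-arm risk ratio on a population selected after randomisation by an event that HBV0 may affect. That ratio is not a randomised effect, and its error has no fixed direction: 0.82 to 0.86 with 25% more non-fatal admissions, 1.17 to 1.24 with 22% fewer, and 1.00 when added admissions are as fatal as the usual ones and deaths rise. The first two ranges rest on the plan's 2.6% and 1.4%, on an assumed 25% to 100% of deaths in hospital, and on deaths unaffected by HBV0.

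The disagreement on sepsis is a plain inconsistency between Table 2 and 8.3. Both matters are of minor to moderate priority. Neither touches the primary or secondary outcomes.

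**What to change.** 1. In Table 2, 8.2 and 8.3, add in-hospital death per randomised infant, all-cause and infectious, as the between-arm comparison. State that out-of-hospital death is a competing event, for example with a cause-specific Cox model stratified by sex and place of enrolment like the primary analysis.
2. Keep case-fatality among admitted infants, including by disease group, labelled as descriptive and conditional on admission.
3. Use one identical list of disease groups in Table 2 and 8.3, containing both sepsis and neonatal conditions other than sepsis, and state in both places whether case-fatality by disease group is planned.

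The cost is wording in three places. Deaths, admissions, diagnoses and admission outcomes are already collected (4.2), and the sample size is unaffected.

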9 DATA MANAGEMENT

9.1 Data Collection

Data collection will be undertaken by the researchers and entered in trial databases by data entry clerks at the Bandim Health Project.

9.2 Data Storage

Data will be stored on site-specific departmental password-protected computer files and analyzed in de-identified but re-identifiable form. The de-identified trial database used by the trial statistician to conduct the final data analysis of the trial will be uploaded to a public repository at the time of paper publication.

9.3 Study Record Retention

The Investigator shall maintain all essential trial documents and source data. All records - including signed Informed Consent Forms, Case Report Forms (CRFs), and the Investigator Site File - will be archived in a secure, fire-protected location for a minimum of 20 years following the completion or discontinuation of the study. No records shall be destroyed without prior written authorization from the Sponsor. If the Investigator can no longer maintain the records (e.g., due to retirement or site closure), custody must be transferred to an appropriate person or facility, and the Sponsor must be notified in writing of the new location.

10 ADMINISTRATIVE ASPECTS

10.1 Confidentiality

The Investigator must ensure that the privacy of all study participants is maintained in accordance with applicable data protection laws. All reports and data communication will identify participants only by a unique Subject Identification Code.

By signing the Informed Consent Form, participants authorize monitors, auditors, and regulatory authorities to access their source medical records for data verification purposes. All study results intended for publication will be strictly anonymized.

10.2 Modifications of the trial protocol

Potential necessary modifications of the trial protocol will be communicated to the DSMB and sent for ethics approval prior to implementation.

10.3 Participant Reimbursement

There will be no reimbursement for the participants.

10.4 Financial Disclosure and Conflicts of Interest

None of the investigators have a financial disclosure or conflict of interest to disclose.

11 USE OF DATA AND PUBLICATIONS POLICY

The trial results will be published in peer-reviewed journals. A summary in Portuguese and a copy of the trial report will be sent to the library of the National Institute of Health in Guinea-Bissau (INASA) and the results will be communicated to the National Committee of Ethics in Guinea-Bissau.

12 ETHICAL CONSIDERATIONS

The trial will be conducted in adherence to the ethical standards outlined in the Declaration of Helsinki. The ethical committee of Guinea-Bissau has approved the trial design, informed consent process, data collection forms and safety measures.

Information about the trial will be provided in clear, understandable language considering the cultural and educational background of the mother/guardian, and the difficulties surrounding childbirth in Guinea-Bissau. It will be ascertained that parents or guardians fully understand the implications of trial participation.

It will be explained that all invited neonates (regardless of consent to participate) are entitled to free consultations at the three health centers located within the HDSS of the Bandim Health Project, in Bandim, Belém and Cuntum. Children presenting for consultation will be given access to essential medications free of charge. BCG and OPV vaccination will be offered to newborns that are ineligible to participate or where the mother/guardian declined participation. Participants in the trial will be covered via the collateral insurance agreement of the University of Southern Denmark.

For the subgroup of children participating in the neurodevelopmental assessment, it will be emphasized that the results can help identify a child's strengths and areas where they might need additional support. Testing can help identify potential learning difficulties early on, allowing for timely interventions and support. It will be explained that cognitive tests are not the sole measure of a child's intelligence or potential. They provide a snapshot of specific cognitive skills at a particular time. Parents will be reassured that there is no need for children to prepare for the tests, and that the aim is to understand their current abilities, not to catch them out. It will be made clear that results are kept strictly confidential.

For the subgroup of children participating in the assessment of AD (due to an itchy rash), they will have access to a study MD with specialized training in diagnosing and treating atopic AD.

The trial will examine the broader health effects of HBV0 - a widely administered neonatal vaccine that is universally recommended by the WHO, also to neonates weighing below 2,000 grams and to premature neonates. We will use a HBV0 vaccine that has been evaluated and approved by WHO (pre-qualification) to meet international standards of quality, safety and efficacy.

Half of the participants will receive HBV0 which they would otherwise not have received. HNSM is currently the only Maternity Center in urban Bissau where BCG and OPV are routinely administered daily, although not on weekends and public holidays. As a consequence of the trial, more children will have timely vaccination opportunities, as BCG and OPV vaccines will be provided within 7 days after birth at all recruitment centers on each weekday. Vaccination of these newborns would otherwise often be delayed and procuring vaccination in Guinea-Bissau can be associated with a financial burden for the household.[59,60] Given that RCTs indicate beneficial

non-specific effects of both BCG[1] and OPV[15], all participants are thus expected to benefit from their participation in the trial. While the protective specific effect of HBV0 is well-established, the broader effects of HBV0 have never been investigated. With established certainty regarding the beneficial specific effects of HBV0 in regard to vertical transmission of hepatitis B, absence of tangible benefit for babies born to HBsAg-negative mothers, no trials comparing BCG+OPV vs BCG+OPV+HBV0 and uncertainty regarding the short-term and long-term broader health effects of HBV0, there is equipoise for an RCT. Whether the trial identifies that HBV0 is associated with positive, negative or no non-specific effects, it will be of high importance for vaccine policy, providing crucial input on how to best reduce child mortality and morbidity. The trial will provide local and global health authorities and immunization stakeholders updated data of the burden of hepatitis B disease in Guinea-Bissau and the overall health effects associated with HBV0. Such data will be the best way to maintain vaccine confidence in the long run.

13 APPENDIX

13.1 Trial Inclusion Form.

Regno (birth number, HNSM): _____ Adhesive study number: _____ Written study number: _____

Date ____/____/20____ Inclusion assistant: _____ Place of enrollment: _____

The child already received a vaccine: Yes____ No____ Is sick or has a malformation: Yes____ No____

Age ≤1 week: Yes____ No____ Can be included: Yes____ No____

Information about the parents

Relation to the child ____ (1: Mother, 2: Father, 3: Uncle/aunt, 4: grandparent, 5: Other)

The mother is alive: Yes____ No____ If no, date of death: ____/____/202____

Mother's name _____

Telephone number, Orange: _____ Telephone number, Airtel: _____

Does not have a telephone____ Does not remember telephone number____ House name _____

Age____ Ethnicity_____ Schooling_____ From BHP area Yes____ No____ BHP address

information: Neighborhood and zone (TaBz)_____ House number (CaMo)_____ Child ID

(CNO)_____ Neighborhood (if not BHP area)_____

Mother's place of birth_____

Father's name _____

Telephone number, Orange: _____ Telephone number, Airtel: _____

Does not have a telephone____ Age____ Ethnicity_____ Went to school

Yes____ No____ Unknown____ Father lives with mother Y____ N____

Other contacts and relation to the child

Name contact 1 _____ Relation _____ N° _____

Name contact 2 _____ Relation _____ N° _____

Name contact 3 _____ Relation _____ N° _____

Measurements

Mother: Arm circumference____ mm Has BCG scar Yes____ No____ Width____ Height____ Assistant____

Father: Arm circumference____ mm Has BCG scar Yes____ No____ Width____ Height____ Assistant____

Information about the child

Name (if named) _____ Birth date ____ / ____ /202 ____

Time of birth ____ : ____ birthplace _____ C-section Yes ____ No ____

Sex Male ____ Female ____ Twin Yes ____ No ____ Twin number _____ Twin study number _____

Height ____ Head circumference ____ Admitted before enrolment Yes ____ No ____ Where _____

If admitted, date of hospital admission ____ / ____ /20 ____ Date of discharge ____ / ____ /20 ____

Birth weight _____ Weight on day of inclusion _____

Confirmed the child's sex (assistant name): _____

The mother or guardian of the child provided consent for participation in the trial: Yes ____ No ____

Observations _____

Randomization

Date of randomization ____ / ____ /202 ____ Time of randomization ____ : ____

Randomization lot number _____

Randomization result: HBV0 _____

Randomization result: No HBV0 _____

Date of HBV0 vaccination: ____ / ____ / 202 ____ Time ____ : ____ Batch **HBV0**: _____ Expiry ____ /202 ____

Date of BCG vaccination: ____ / ____ / 202 ____ Time ____ : ____ Batch **BCG**: _____ Expiry ____ /202 ____

Date of OPV vaccination: ____ / ____ / 202 ____ Time ____ : ____ Batch **OPV0**: _____ Expiry ____ /202 ____

BCG vaccination papule: Height ____ mm Width ____ mm Vaccinator: _____

BCG vaccine strain administered: ____ (Denmark: 1, Japan: 3, Bulgaria: 5, Russia: 8)

Confirmed by: _____

